7.4.8. Malignancy Relapse-Related Mortality Rate

Malignancy relapse-related mortality rate is defined as the proportion of subjects whose malignancies relapse and have a fatal outcome. Incidence of such events will be tabulated with summary statistics.

7.4.9. Failure-Free Survival

Failure-free survival is defined as the proportion of subjects who are still alive, have not relapsed of underlying hematologic disease, have not required additional therapy for aGVHD, and have not had signs or symptoms of cGVHD. Subjects without an event of relapse of underlying hematologic disease, death due to relapse, death due to causes other than relapse, initiation of new anti-GVHD therapy, or signs or symptoms of cGVHD will be censored at the date of study withdrawal or the date of last contact before or on the data cutoff date, whichever is earlier. After randomization, the FFS event date will be the first occurrence of one of the following:

- Initiation of anti-GVHD therapy, or
- Relapse/recurrence of underlying hematologic disease, or
- Death due to malignancy relapse, or
- Death due to causes other than malignancy relapse, or
- Signs or symptoms of cGVHD.

Failure free survival will be analyzed according to the randomized treatment group and strata assigned at randomization.

The survival distribution of FFS in each treatment group overall [REDACTED] will be estimated using the KM method, and the KM curves; medians; 1-, 2-, 6-, 12-, 18-, and 24-month (at Days 30, 60, 180, 365, 547, and 730, respectively) survival estimates, and 95% CIs will be presented (Brookmeyer and Crowley 1982). The hazard ratio of treatment relative to placebo overall [REDACTED] will be calculated, along with its 95% CI, using a stratified Cox model. Stratified log-rank test will also be used to test FFS survival curve in the itacitinib group against the placebo group.

Subgroup KM analyses of FFS will also be conducted by Day 28 response status [REDACTED]

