### 9.3. Level of Significance

The 1-sided significance level for the primary and key secondary endpoint analysis is 0.025. The 2-sided significance level for other analyses is 0.05. All CIs will be 95%.

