#### 9.4.2. Secondary Analyses

The key secondary endpoint is NRM at Month 6, defined as the proportion of subjects who died due to causes other than malignancy relapse at Month 6. The comparison of NRM at Month 6 between treatment cohorts will be conducted using a 2-sample proportion test with normal approximation. Summary statistics and 95% CI will be provided.

Additional secondary endpoints will be analyzed as follows:

- ORR, defined as the proportion of subjects demonstrating a CR, VGPR, or PR at Days 14, 56, and 100. The comparison between treatment cohorts will be conducted using a 2-sample proportion test with normal approximation. Summary statistics and applicable 95% CI will be provided.
- NRM, defined as the proportion of subjects who died due to causes other than malignancy relapse at Months 9, 12, and 24. The comparison between treatment cohorts will be conducted using a 2-sample proportion test with normal approximation. Cumulative incidence rates will be provided. Summary statistics and applicable 95% CI will be provided.
- DOR, defined as the time from first response until GVHD progression or death. The comparison between treatment cohorts will be conducted using the log-rank test. The Kaplan-Meier method will be used. Summary statistics will be provided.
- TTR, defined as the interval from treatment initiation to first response.
- Relapse rate of malignant and nonmalignant hematologic diseases, defined as the proportion of subjects whose underlying disease relapses. The comparison between treatment cohorts will be conducted using a 2-sample proportion test with normal approximation. The cumulative incidence rate and summary statistics will be provided.

- Relapse-related mortality rate, defined as the proportion of subjects whose malignancy relapses and has a fatal outcome. The comparison between treatment cohorts will be conducted using a 2-sample proportion test with normal approximation. The cumulative incidence rate and summary statistics will be provided.
- FFS, defined as the proportion of subjects who are still alive, have not relapsed, have not required additional therapy for aGVHD, and have not demonstrated signs or symptoms of cGVHD, at Month 6. The comparison between treatment cohorts will be conducted using the log-rank test. The Kaplan-Meier method will be used. Summary statistics will be provided.

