2.2. Study Objectives and Endpoints

[Table 1](#) presents the study objectives and endpoints.

Table 1: Objectives and Endpoints

Primary Objective	Primary Endpoint
Compare the efficacy of itacitinib in combination with corticosteroids versus placebo in combination with corticosteroids in terms of ORR at Day 28 in subjects with aGVHD.	ORR at Day 28, defined as the proportion of subjects demonstrating a CR, VGPR, or PR.
Key Secondary Objective	Key Secondary Endpoint
Compare the efficacy between treatment cohorts at a subsequent key clinical landmark.	NRM at Month 6, defined as the proportion of subjects who died due to causes other than malignancy relapse at Month 6.
Secondary Objectives	Secondary Endpoints
Compare additional response and longer-term efficacy outcomes between treatment cohorts.	ORR, defined as the proportion of subjects demonstrating a CR, VGPR, or PR at Days 14, 56, and 100.
	NRM at Months 9, 12, and 24.
	DOR for responders will be calculated. The DOR is defined from the time of the onset of response to loss of response. Subjects who died or discontinued will be censored at the death date or the previous assessment.
	TTR, defined as the interval from treatment initiation to first response.
	Relapse rate of malignant and nonmalignant hematologic diseases, defined as the proportion of subjects whose underlying hematologic disease relapses.
	Malignancy relapse-related mortality rate, defined as the proportion of subjects whose malignancy relapses and has a fatal outcome.
	FFS, defined as the proportion of subjects who are still alive, have not relapsed, have not required additional therapy for aGVHD, and have not demonstrated signs or symptoms of cGVHD, at Month 6.
OS, defined as the interval from study enrollment to death due to any cause.	
Assess the incidence and severity of AEs and SAEs.	Clinical safety data (eg, AEs, infections) will be tabulated and listed.
Evaluate the PK of itacitinib when administered in combination with corticosteroids.	C_{max} , C_{min} , t_{max} , AUC, and CL/F.
Evaluate the incidence of secondary graft failure.	Incidence rate of secondary graft failure, defined as > 95% recipient cells any time after engraftment with no signs of relapse, OR retransplantation because of secondary neutropenia ($< 0.5 \times 10^9/L$) and/or thrombocytopenia ($< 20 \times 10^9/L$) within 2 months of transplant.

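### Failure-free survival is defined as a Month 6 proportion, but the only between-arm analyses described for it use all follow-up, so its p-value and hazard ratio do not answer the stated endpoint.

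*SAP*

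**What the plan says.** **Endpoint.** Protocol Section 2, Protocol 9.4.2 and SAP Table 1 (Section 2.2) all make FFS the proportion of subjects alive, without relapse, and who "have not required additional therapy for aGVHD, and have not demonstrated signs or symptoms of cGVHD, at Month 6".

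**Analysis.**
- Protocol 9.4.2 puts that Month 6 definition and a log-rank test in the same bullet: "The comparison between treatment cohorts will be conducted using the log-rank test".
- SAP 7.4.9 restates the definition without the time point and treats FFS as time to first event. Subjects without an event are "censored at the date of study withdrawal or the date of last contact before or on the data cutoff date", whichever is earlier. No cut is made at Day 180.
- SAP 7.4.9 plans KM curves and estimates up to "24-month (at Days 30, 60, 180, 365, 547, and 730, respectively) survival estimates, and 95% CIs will be presented".
- The arms are compared by a stratified Cox model ("The hazard ratio of treatment relative to placebo overall") and by the log-rank test: "Stratified log-rank test will also be used to test FFS survival curve in the itacitinib group against the placebo group".

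**Error control.** Protocol 9.3 states "The 2-sided significance level for other analyses is 0.05". SAP 3.2 applies no multiplicity adjustment beyond the primary and key secondary endpoints.

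**The concern.** A log-rank test or Cox model run to the data cutoff weighs every event, whenever it occurs. A Month 6 proportion depends only on what happens up to Day 180. The p-value and hazard ratio that would be reported for FFS therefore address whether the whole curves differ, and the endpoint table asks a different question.

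Follow-up beyond Month 6 will be substantial. The final analysis waits for the last subject's Day 180 visit (SAP Section 3), so subjects enrolled earlier contribute later time. How much they contribute depends on accrual speed, which is no part of the endpoint.

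The plan also expects events after Month 6. Chronic GVHD is an FFS component and is summarized at Day 365 as well as Day 180 (SAP 7.5). Taper of study drug normally starts at Day 180 (Protocol 5.4.3), and re-treatment with open-label itacitinib can follow a completed taper (Protocol 6.4). SAP 7.1 names such re-treatment as new anti-GVHD therapy only for subjects first given placebo, and new therapy is an FFS event.

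What is at stake is the reading of one secondary endpoint.

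**Working it through.** **1. Is there a planned figure to reproduce?** No. Neither document gives an FFS rate, effect size or power. The sample size to use is 436, or 218 per arm (SAP 3.3: 414/0.95 = 435.8, rounded up to 436).

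**2. How much later follow-up is there?** SAP 5.3 dates the Interim 1 cutoff, when 112 subjects had completed Day 28 or withdrawn, at 25 June 2018, and the Interim 2 cutoff at 17 April 2019. The gap is 296 days. Subjects among those 112 still being followed were then at about Day 28 + 296 = 324 or later, and will be further on at the final analysis.

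**3. Day 180 comparison by formula.** Assume FFS of 30% v 42% at Month 6 and no loss before Day 180, so that KM equals the simple proportion.
- SE = √[(0.30×0.70 + 0.42×0.58)/218] = √(0.4536/218) = 0.0456
- z = 0.12/0.0456 = 2.63
- Power at one-sided 0.025 = Φ(2.63 − 1.96) = Φ(0.67) = 0.75

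Nothing after Day 180 enters this figure.

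**4. Whole-curve log-rank by simulation.** Assumptions, none of them from the documents: constant hazard up to Month 6, a second constant hazard afterwards, and follow-up uniform over 6 to 24 months. There are 218 subjects per arm, and both tests are unstratified at one-sided 0.025. Entries are the proportion of trials favouring itacitinib.

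| Month 6 FFS, placebo v itacitinib | Later hazard per month, placebo v itacitinib | Log-rank, all follow-up | Day 180 KM difference |
|---|---|---|---|
| 30% v 42% | 0.08 v 0.08 | 0.68 | 0.75 |
| 40% v 50% | equal | 0.45 | 0.54 |
| 40% v 40% | 0.08 v 0.06 | 0.08 | 0.02 |
| 40% v 40% | 0.10 v 0.05 | 0.29 | 0.02 |
| 40% v 50% | 0.06 v 0.08 | 0.22 | 0.56 |
| 40% v 50% | 0.05 v 0.10 | 0.05 | 0.54 |

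The first two rows are the neutral case. The fourth and last rows are deliberate extremes.

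**5. Second set of assumptions.** This used uniform accrual over 600 days, follow-up capped at 730 days, 5% dropout by Day 180, two-sided 0.05 and 4,000 trials per scenario.
- No difference at any time: both tests reject in 5.1%.
- 40% v 53% at Month 6 with the same later hazard: log-rank 67%, Day 180 78%.
- Over all scenarios run, 18–43% of FFS events fell after Day 180.

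The pattern matches step 4.

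**The case against.** The other side has a good case on weight.

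- **Month 6 is reported.** Each arm gets a Day 180 KM estimate with a 95% CI. A reader might infer that the stated endpoint goes unanalysed. It does not: what is missing is one contrast with its interval and p-value. This stands.
- **No confirmatory claim depends on it.** A reader might infer that late events could create or erase a trial conclusion. Only Day 28 ORR and Month 6 NRM are alpha-controlled, and FFS is outside that family. This stands.
- **The SAP did not introduce the log-rank test.** Protocol 9.4.2 already pairs it with the Month 6 definition, so the mismatch belongs to both documents. The SAP's own contribution is to drop the time point in 7.4.9 without listing this in 10.1.
- **The log-rank test is valid.** It holds its level as a test of equal curves. The fault is only that it tests something other than the defined endpoint.
- **The striking simulation results are constructed.** They need hazards that separate sharply at exactly Month 6, which no document supports. They show that disagreement is possible and do not predict it. The milder reversal (0.22 against 0.56) is still sizeable, however.
- **Absence cannot be fully shown.** SAP 7.4.9 has redactions, and the efficacy part of the Appendix B table list is not in the available text. A Month 6 comparison table cannot be excluded, although the methods text describes none.

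None of this reconciles the Month 6 definition with an untruncated test.

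**Conclusion.** The mismatch is real and minor. Followed as written, the plan gives a p-value and hazard ratio for FFS that answer a whole-curve question, with no described between-arm comparison at Month 6. If hazards are equal after Month 6, the cost is a modest loss of power: 0.68 against 0.75, or 0.45 against 0.54, in the illustrations. If the arms diverge or cross later, the two analyses can disagree. In the direction of a difference absent at Month 6, the log-rank rate runs from about 0.08 to 0.29 against 0.02, depending on how strongly the later hazards differ. These sizes rest on assumed FFS rates, later hazards and follow-up. The mismatch itself rests on the text alone. The primary and key secondary conclusions and the familywise error rate are unaffected.

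**What to change.** In SAP 7.4.9, name the comparison for the Month 6 endpoint as the risk-stratified difference in Day 180 KM FFS. For stratum j, let D_j be the itacitinib minus placebo KM estimate at Day 180 and V_j the sum of the two Greenwood variances. With stated weights w_j summing to 1:

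- D = Σ w_j D_j
- SE = √(Σ w_j² V_j)
- z = D/SE, and 95% CI = D ± 1.96 SE

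Use the same w_j for test and interval. This needs saying because the Day 180 KM method for NRM in SAP 7.4.1.2, the natural template, sums strata unweighted in the test and uses inverse-variance weights in the interval. Death and relapse are themselves FFS events, so KM raises no competing-risk difficulty here. Keep the log-rank test and Cox model as supportive whole-curve analyses.

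The cost is a few lines of text and no new data, since the Day 180 estimates are already planned. The small downside is that later events do not count in the Month 6 comparison.

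If the whole curve is what the sponsor wants, the alternative is to redefine FFS as a time-to-event endpoint in SAP Table 1 and Protocol Sections 2 and 9.4.2, and declare the change in SAP 10.1. Either route resolves the conflict.

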7.4.10. Overall Survival

Overall survival is defined as the time from randomization to death due to any cause during the study. The KM method will be used to estimate the survival time distribution and the median survival. Subjects with no observed death or loss to follow-up will be treated as censored at either the date of study withdrawal or the date of last contact prior to or on the data cutoff date, whichever is later.

Overall survival will be analyzed according to the randomized treatment group and strata assigned at randomization.

The survival distribution of OS in each treatment group overall [REDACTED] will be estimated using the KM method, and the KM curves; medians; 1-, 2-, 6-, 12-, 18-, and 24-month (at Days 30, 60, 180, 365, 547, and 730, respectively) survival estimates, and 95% CIs will be presented (Brookmeyer and Crowley 1982). The hazard ratio of itacitinib relative to placebo overall [REDACTED] will be calculated, along with its 95% CI, using a stratified Cox model. Stratified log-rank test will also be used to test the OS survival curve in the itacitinib group against the placebo group.

Subgroup KM analyses of OS will also be conducted by Day 28 response status [REDACTED].

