### **6.5.3. Survival Follow-Up**

Subjects who complete post-treatment follow-up or experience GVHD progression or require a new anti-GVHD therapy should be contacted by telephone, email, or visit at least every 8 weeks ( $\pm 7$  days) to assess for new GVHD therapy and survival status until death, withdrawal of consent, or the end of the study, whichever occurs first.

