4.1.7. Date of Last Contact

The date of last contact is defined at the subject level as the latest date of discontinuation, laboratory assessment, GVHD/ECOG assessment, vital sign, ECG, scheduled or unscheduled visit, and any available date in the clinical database showing that the subject is still alive prior to or on the clinical data cutoff date.

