$\widehat{CDF}_{pbo,j}(t = D180)$ and $SE(\widehat{CDF}_{pbo,j}(t = D180))^2$ are the cumulative distribution function estimate at Day 180 in the placebo group in the jth stratum and its variance, respectively.

$\widehat{CDF}_{trt,j}(t = D180)$ and $SE(\widehat{CDF}_{trt,j}(t = D180))^2$ are defined similarly in the itacitinib group for jth stratum subjects. $TS_{Day180NRM}$ will be asymptotically distributed as a Chi-square test statistic with degree of freedom equal to 1.

The overall estimate of treatment difference in Day 180 NRM between placebo and itacitinib is thus defined as the following:

$$w * [\widehat{CDF}_{pbo,standard}(t = D180) - \widehat{CDF}_{trt,standard}(t = D180)] + (1 - w) * [\widehat{CDF}_{pbo,high}(t = D180) - \widehat{CDF}_{trt,high}(t = D180)]$$

Its 95% CI is the above estimate of difference

$$\pm 1.96 * \sqrt{w^2 * (SE(\widehat{CDF}_{pbo,standard}(t = D180)))^2 + (SE(\widehat{CDF}_{trt,standard}(t = D180)))^2 + (1 - w)^2 * (SE(\widehat{CDF}_{pbo,high}(t = D180)))^2 + SE(\widehat{CDF}_{trt,high}(t = D180))^2)}$$

with weight w defined by inverse of variance in two baseline GVHD risk groups. That is:

$$w = \frac{1/[SE(\widehat{CDF}_{pbo,standard}(t=D180))^2 + SE(\widehat{CDF}_{trt,standard}(t=D180))^2]}{1/[SE(\widehat{CDF}_{pbo,standard}(t=D180))^2 + SE(\widehat{CDF}_{trt,standard}(t=D180))^2] + 1/[SE(\widehat{CDF}_{pbo,high}(t=D180))^2 + SE(\widehat{CDF}_{trt,high}(t=D180))^2]}$$

In order to conduct above hypothesis testing for NRM at Day 180, time to NRM, defined as the interval between randomization and death due to causes other than malignancy relapse, will be derived. All subjects in the FAS without a death due to causes other than malignancy relapse will be censored at either study withdrawal, death due to malignancy relapse, or the date of last contact before or on the cutoff date, whichever is earliest.

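### The OS censoring rule can carry a lost subject past the last date known alive, and its wording leaves the rule for lost subjects unclear

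*SAP*

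**What the plan says.** SAP 7.4.10 defines OS from randomization to death from any cause. It plans Kaplan-Meier estimates to 24 months, a stratified log-rank test and a stratified Cox hazard ratio. Censoring is at "either the date of study withdrawal or the date of last contact prior to or on the data cutoff date, whichever is later". The sentence opens: "Subjects with no observed death or loss to follow-up will be treated as censored".

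SAP 4.1.7 defines the date of last contact as a maximum over several dates. It begins with "the latest date of discontinuation, laboratory assessment, GVHD/ECOG assessment", continues through vital signs, ECGs and visits, and ends with any database date up to the cutoff that shows the subject alive.

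The neighbouring time-to-event endpoints take the other end of the pair. Failure-free survival (SAP 7.4.9) is "censored at the date of study withdrawal or the date of last contact before or on the data cutoff date, whichever is earlier". Time to NRM (SAP 7.4.1.2) is censored at "study withdrawal, death due to malignancy relapse, or the date of last contact before or on the cutoff date, whichever is earliest". SAP 7.1 and the competing-risks analyses in SAP 7.4.3 follow the same pattern. The SAP gives no reason for the difference, and its change list (10.2.1) does not mention it.

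Under Protocol 6.5.3, subjects in survival follow-up "should be contacted by telephone, email, or visit at least every 8 weeks", with a 7-day window. Under Protocol 6.5.2, those who stopped treatment for reasons other than GVHD progression are first seen every 28 days.

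**The concern.** A censoring date should be the last date on which the subject could have been observed to be alive. For a subject who stops responding, the withdrawal date on the form may be the day the site closed the record, which can fall after the last visit or call. A rule that takes the later of that date and the last contact then counts the gap as event-free time. No death could be seen in the gap, so the risk set is inflated and survival is overstated.

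The definition of last contact does not protect against this, because it admits the discontinuation date whether or not anyone saw the subject alive that day.

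The opening words of the OS sentence add a second problem. They can be read as covering everyone without an observed death, including those lost. They can also be read as covering only subjects with neither a death nor a loss. On the second reading, lost subjects have no stated rule, and they are the ones for whom the choice of date matters.

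**Working it through.** The documents give no power, event count or effect size for OS, so there is no plan figure to reproduce. Two checks were made.

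**1. Date logic.** Let W be the withdrawal date, A the last date with evidence of life and LC the last contact under SAP 4.1.7. The word *discontinuation* in 4.1.7 has two readings:

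- leaving the study, so LC = max(W, A);
- stopping treatment, so W does not enter. If treatment stopped no later than A, LC = A.

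The days below are examples.

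| Example subject | Reading of 4.1.7 | LC | Earlier of W and LC | Later of W and LC (OS rule) | Last known alive |
|---|---|---|---|---|---|
| Withdrew Day 100, known alive Day 150 | either | 150 | 100 | 150 | 150 |
| Last alive Day 100, withdrawal recorded Day 163 | leaving the study | 163 | 163 | 163 | 100 |
| Last alive Day 100, withdrawal recorded Day 163 | stopping treatment | 100 | 100 | 163 | 100 |
| Ongoing, last seen Day 200 | either | 200 | 200 | 200 | 200 |

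For the lost subject, OS overruns by 163 − 100 = 63 days on both readings. On the first reading the earlier-date rule overruns equally. For the subject known alive after withdrawal, the OS rule gives the right date and the earlier-date rule drops 150 − 100 = 50 days of known survival.

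**2. Size, by illustration.** Inputs:

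- Day 180 mortality m = 33% or 19.8%. These are the NRM planning rates in SAP 3.3, used here as a stand-in for OS.
- Fraction lost f = 5%. This is the early-withdrawal allowance in SAP 3.3. It is stated for subjects without response data before Day 28, so applying it to OS is an assumption.
- Gap g = 56 days (8 weeks) or 63 days (8 weeks plus the 7-day window), from Protocol 6.5.3.
- Exponential mortality, losses uniform over 180 days, and every lost subject carried the full gap. All three are assumptions.

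With λ = −ln(1 − m)/180:

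- truly at risk: R(t) = e^(−λt) · (1 − f·t/180)
- carried but unobservable: P(t) = [f/(180λ)] · (e^(−λ·max(0, t−g)) − e^(−λt))
- apparent hazard: λ·R/(R + P)
- apparent mortality: 1 − exp(−∫ apparent hazard over 0 to 180)

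For m = 33%, f = 5% and g = 63, λ = 0.002225. At Day 180, R = 0.67 × 0.95 = 0.6365 and P = 0.0126, so the hazard is read at 0.6365/0.6491 = 0.981 of its true value. Integrating over the 180 days gives:

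| True mortality | Lost | Gap (days) | Apparent mortality | Understated by (points) |
|---|---|---|---|---|
| 33% | 5% | 56 | 32.62% | 0.38 |
| 33% | 5% | 63 | 32.58% | 0.42 |
| 19.8% | 5% | 56 | 19.56% | 0.24 |
| 19.8% | 5% | 63 | 19.53% | 0.27 |
| 33% | 10% | 63 | 32.15% | 0.85 |
| 19.8% | 10% | 63 | 19.25% | 0.55 |
| 33% | 20% | 120 | 30.27% | 2.73 |
| 19.8% | 20% | 120 | 18.09% | 1.71 |

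A simulation of 400,000 subjects per setting agrees. With 5% lost and a 63-day gap it reads 32.6% and 19.5%; with lost subjects censored at the last date known alive, it returns the assumed 33% and 19.8% within simulation error. A separate 12-month simulation used six-month mortality of 30 to 40%, losses spread over a year, 5% lost and an 8-week gap. It overstates OS by about 0.3 points. The rows with 10% or 20% lost, and the 120-day gap, have no source in the documents and show only how the effect scales.

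**The case against.** The strongest reply is that the contrast between later and earlier is not what does the harm. SAP 4.1.7 is itself a maximum that includes discontinuation. If that means leaving the study, last contact never precedes withdrawal: the OS rule collapses to last contact, the NRM and FFS rules collapse to the withdrawal date, and a loss recorded late overruns equally in all three. For a subject known alive after withdrawal, later is the better word. This stands. A reader might infer from the wording that lost subjects necessarily get one date for NRM and FFS and a later one for OS. The documents do not support that: it holds only if discontinuation in 4.1.7 means stopping treatment. SAP 6.2 and 8.2.2 do separate stopping treatment from leaving the study, but 4.1.7 does not say which it means. On either meaning, the OS date can still pass the last evidence of life.

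A second reply is that the overrun depends on how sites date the withdrawal of a lost subject, which neither document states, and that a consent withdrawal made in person is itself evidence of life. This also stands. It confines the problem to losses and makes the size conditional.

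A third is that different endpoints may properly have different censoring dates. This is right for FFS. Its events include signs of chronic GVHD, and the schedule of assessments has no chronic GVHD assessment in the survival follow-up column. Carrying FFS to the last date known alive would keep subjects at risk while a component event was not being looked for.

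**Conclusion.** The point holds as a defect in the written rule. SAP 7.4.10 together with 4.1.7 allows OS follow-up to be credited after the last date known alive, and the sentence is ambiguous about lost subjects. Whether any subject is affected depends on how withdrawal dates are recorded.

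With 5% lost and a 63-day gap, Day 180 mortality is understated by about 0.3 to 0.4 points; at 56 days the range is about 0.2 to 0.4. This rests on the planning NRM rates standing in for OS mortality and on every lost subject being carried the full gap. The effect is larger only under larger assumed losses or gaps.

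A reader might also infer a bias between arms, since unequal losses would distort the comparison. The documents give no loss rates by arm, so neither its existence nor its direction is established.

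OS is a secondary endpoint without multiplicity adjustment (SAP 3.2). The Day 28 ORR test is a stratified CMH test on a binary outcome, and the primary Month 6 NRM analysis is a stratified CMH test on proportions (SAP 7.4.1.1). Neither uses this censoring date.

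**What to change.** In SAP 7.4.10, replace the censoring sentence with: *Subjects without a death dated on or before the cutoff, including those lost to follow-up, are censored at the last date known alive on or before the cutoff.*

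In SAP 4.1.7, count a discontinuation or withdrawal date only if the subject was seen or contacted alive on that date, and say whether discontinuation means treatment or study.

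Do not substitute the earlier-date rule in 7.4.10.

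The time-to-event NRM analyses (SAP 7.4.1.2, 7.4.2 and 7.4.3) can use the same last-known-alive date for subjects with no event. With common dates, the NRM and relapse-death cumulative incidences in competing-risks analysis II sum to one minus the Kaplan-Meier OS estimate, so the tables reconcile. FFS should keep a censoring date tied to when its component events were last assessed, with a line saying why it differs.

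The cost is a few sentences and one derived date. No new data are collected beyond knowing whether a recorded withdrawal involved contact with the subject. OS estimates may come out slightly less favourable.
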